10.4. Vital Signs

Descriptive statistics of observed values will be presented for vital sign data at each visit (Day 1, Day 8, and Day 15), including systolic BP (mmHg), diastolic BP (mmHg), and HR (bpm) by treatment group and overall. Changes from baseline (Day 1) to each scheduled post-baseline time point will be presented.

10.5. IOP

Observed values and change from baseline in IOP will be summarized descriptively using counts and percentages for each treatment group at each visit (Day 1, Day 8, and Day 15) for the observed value and change from baseline (Day 1). Separate summaries will be created for the study eye, the non-study eye, and the best of either eye. Treatments will be compared using the same ANCOVA model proposed for the continuous secondary efficacy endpoints.

10.6. Biomicroscopy and Ophthalmoscopy

Results from biomicroscopic and ophthalmoscopic examinations at Day 1 and Day 15 will be summarized by treatment group.

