5 SUBJECT INCLUSION AND EXCLUSION CRITERIA

5.1 Subject Inclusion Criteria

1. Males or females \geq 18 years of age
2. Subject-reported DLD (likely subjects with a history of multifocal IOLs, post-laser-assisted in situ keratomileusis [LASIK], corneal scars, and keratoconus)
3. Ability to comply with all protocol-mandated procedures independently and to attend all scheduled office visits
4. Otherwise healthy and well-controlled subjects
5. Able and willing to give written consent to participate in this study
6. Able to self-administer study medication
7. [REDACTED]
8. \leq 30 Early Treatment Diabetic Retinopathy Study (ETDRS) letters (20/63 Snellen or worse) in mLCVA score in at least one eye using the [REDACTED]
9. [REDACTED]

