5.2 Subject Exclusion Criteria

Excluded from the study will be individuals with the following characteristics:

Ophthalmic (in either eye):

1. Prior unresolved dry eye diagnosis, taking prescription drops for dry eye, or taking artificial tear drops routinely for dry eye
2. Prior history of fluctuating vision
3. Clinically significant ocular disease as deemed by the Investigator (e.g., untreated cataract, glaucoma, corneal edema, uveitis, severe keratoconjunctivitis sicca, retina degeneration, loss of visual field due to glaucoma or stroke, branch retinal vein occlusion, retina flare) that might interfere with the study
4. Known hypersensitivity to any topical alpha-adrenoceptor antagonists
5. Known allergy or contraindication to any component of the vehicle formulation
6. History of cauterization of the punctum or punctal plug (silicone or collagen) insertion or removal
7. Ocular trauma, ocular surgery (e.g., IOLs), or laser procedure (e.g., LASIK, photorefractive keratectomy [PRK]) within 6 months prior to screening

8. Use of any topical prescription or over-the-counter (OTC) ophthalmic medications of any kind (including artificial tear drops) within 7 days of screening until study completion, with the exception of lid scrubs with OTC products (e.g., OCuSOFT® lid scrub, SteriLid®, baby shampoo, etc.)
9. Recent or current evidence of ocular infection or inflammation in either eye (such as current evidence of clinically significant blepharitis, conjunctivitis, or a history of herpes simplex or herpes zoster keratitis at screening in either eye). Subjects must be symptom free for at least 7 days.
10. History of diabetic retinopathy, diabetic macular edema, or dry or wet macular degeneration
11. History of any traumatic (surgical or nonsurgical) or non-traumatic condition affecting the pupil or iris (e.g., irregularly shaped pupil, neurogenic pupil disorder, iris atrophy, iridotomies, iridectomy, etc.)
12. Unwilling or unable to discontinue use of contact lenses on their scheduled visits at least 1 hour for soft contact lenses and at least 8 hours for hard gas-permeable contact lenses before ophthalmic assessments at screening, and at least 8 hours (for both types of lenses) before Day 8 and Day 15
13. People with undiagnosed dry eye, at the determination of the Investigator. Dry eye evaluation should be based on one of the following dry eye tests:
 - a. TearLabs osmolarity test (> 308 mOsm/L in either eye or an inter-eye difference ≥ 10 mOsm/L)

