8 ASSESSMENT OF SAFETY

8.1 Specification of Safety Parameters

The assessment of safety and tolerability is the secondary objective of this study. The assessment of safety will be evaluated by:

- Conjunctival hyperemia measured with CCLRU images using a 4-point scale (0-3) ([Appendix 6](#)).
 - None (0) = Normal; appears white with a small number of conjunctival blood vessel easily observed
 - Mild (+1) = Prominent, pinkish-red color of both the bulbar and palpebral conjunctiva
 - Moderate (+2) = Bright, scarlet red color of the bulbar and palpebral conjunctiva
 - Severe (+3) = Beefy red with petechiae, dark red bulbar and palpebral conjunctiva with evidence of subconjunctival hemorrhage
- Biomicroscopy of the anterior segment includes evaluation of cornea, conjunctiva, and anterior chamber. Fluorescein staining will be used.
- IOP is measured with the Tono-Pen.
- Ophthalmoscopy direct or indirect fundus exam without dilation includes optic nerve, macula, vessels, and periphery (note: Use of 90 D lens (indirect) is allowed).
- HR and BP are measured as per the site's normal equipment and procedures.
- AEs
- Brief subject questionnaire ([Appendix 3](#))

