10.3. Conjunctival Hyperemia

Results from the conjunctival hyperemia assessment, measured with a CCLRU card 4-point scale, will be summarized descriptively using counts and percentages for each treatment group at each visit (Day 1, Day 8, and Day 15) for the observed value and change from baseline (Day 1). Separate summaries will be created for the study eye, the non-study eye, and the best of either eye.

Additionally, conjunctival hyperemia will be summarized as a continuous variable. Treatments will be compared using the same ANCOVA model proposed for the continuous secondary efficacy endpoints.

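### SAP 10.6 plans only by-visit results for biomicroscopy and ophthalmoscopy; with baseline corneal findings expected, the biomicroscopy tables cannot show how many subjects developed a new or worsened finding

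*SAP*

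**What the plan says.** SAP Section 10.6 is one sentence: "Results from biomicroscopic and ophthalmoscopic examinations at Day 1 and Day 15 will be summarized by treatment group". It does not mention change, shift, new findings or eye.

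The neighbouring safety sections go further:

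- **Hyperemia (SAP 10.3):** observed values and change from Day 1, separately for the study eye, the non-study eye and the best of either eye.
- **Vital signs (SAP 10.4):** "Changes from baseline (Day 1) to each scheduled post-baseline time point will be presented".
- **IOP (SAP 10.5):** "Observed values and change from baseline in IOP will be summarized descriptively using counts and percentages", with the same split by eye as hyperemia.

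Protocol Section 9.3.6 describes no summary of either examination, so it does not fill the gap.

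On the population, inclusion criterion 2 (protocol 5.1) describes those with self-reported dim light disturbances as "likely subjects with a history of multifocal IOLs, post-laser-assisted in situ keratomileusis [LASIK], corneal scars, and keratoconus". On what is examined, protocol 8.1 says: "Biomicroscopy of the anterior segment includes evaluation of cornea, conjunctiva, and anterior chamber", with fluorescein staining. Ophthalmoscopy covers optic nerve, macula, vessels and periphery. Protocol 7.2.1 and 7.2.3 schedule both examinations at Visit 1 and Visit 3.

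**The concern.** A safety table for an eye drop should let the reader see what appeared or got worse on treatment, by arm. A by-visit count of abnormal findings answers that directly only when few subjects are abnormal at the start. Here a corneal background is expected, so the Day 15 biomicroscopy count will mix old findings with new ones.

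The two visits read together give only a net change, that is, new findings minus resolved ones. A finding that was present at Day 1 and worsened does not move a presence count at all.

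The slit lamp carries particular weight because SAP 10.7 says the dry eye tests, including corneal staining, are done only at Day 1. Biomicroscopy at Day 15 is then the one planned post-dose safety examination of the cornea. Corneal topography is repeated, but it belongs to the OPD-scan data that the protocol treats as exploratory efficacy.

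**Working it through.** **Inputs from the documents.** 136 evaluable subjects, 68 per arm; 15% drop-out between Day 1 and Day 15; about 160 randomized 1:1, so 80 per arm (SAP 6). The plan's own figure reproduces: 136 / (1 − 0.15) = 160. The documents give no baseline prevalence of slit-lamp findings and no expected rate of new ones. Those values below are assumptions, shown over a range.

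**Step 1: what two by-visit counts determine.** In one arm let A be the number abnormal at Day 1, B the number abnormal at Day 15, and n the number examined at both. Then B − A = new − resolved. With A = B, new can be anything from 0 to min(A, n − A). At an assumed 30% background, n = 80 and A = B = 24, so new lies between 0 and min(24, 56) = 24.

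**Step 2: unequal denominators.** With 80 examined at Day 1 and 68 at Day 15, suppose the tables show 24/80 and 20/68, both about 30%. The 12 subjects who left could include 0 to 12 of the 24, so 12 to 24 of the remaining 68 were abnormal at Day 1. The net change in those 68 is then between 20 − 24 = −4 and 20 − 12 = +8, and new findings lie between 0 and 20. Even the net change is not fixed without restricting to subjects with both examinations.

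**Step 3: illustration of how background dilutes a Day 15 comparison.** Assume background b, all persisting, and new findings in 10% versus 2% of subjects without one at Day 1. Day 15 prevalence is b + (1 − b) × rate. For b = 0.30 that is 0.30 + 0.70 × 0.10 = 37.0% versus 0.30 + 0.70 × 0.02 = 31.4%. The shift-table comparison uses n(1 − b) subjects per arm at 10% versus 2%. Power at two-sided 0.05, with p̄ the mean of the two proportions and m subjects per arm, is

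Φ{ [ |p1 − p2| − 1.96 √(2p̄(1 − p̄)/m) ] / √([p1(1 − p1) + p2(1 − p2)]/m) }.

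At b = 0.30 and 80 per arm:

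- Day 15 table: (0.056 − 0.147)/0.0749 = −1.22, power 11%.
- Shift table, m = 56: (0.080 − 0.088)/0.0442 = −0.18, power 43%.

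| Assumed background | Day 15 table, 80 per arm | Shift table, 80 per arm | Day 15 table, 68 per arm | Shift table, 68 per arm |
|---|---|---|---|---|
| 0% | 57% | 57% | 50% | 50% |
| 10% | 24% | 53% | 21% | 46% |
| 30% | 11% | 43% | 10% | 37% |
| 50% | 7% | 32% | 7% | 28% |

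With no background the two tables are equivalent; the loss grows with prevalence. No test of these data is planned, so power here only measures information. It also compares Day 15 alone. A reader who sets Day 15 against Day 1 recovers the net change, which equals new findings if nothing resolves and the same subjects are seen at both visits.

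**Step 4: where a new finding can still be seen.** Protocol 7.2.2 and 7.2.3 have adverse changes recorded as adverse events, and SAP 10.1 tabulates events that begin or worsen on treatment. Protocol 8.3.1 admits an abnormal test result as an adverse event only if it produces signs or symptoms, is judged clinically significant or needs therapy. New findings outside those conditions reach only the by-subject listings (SAP 10).

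**The case against.** The other side has several good points.

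- **Adverse events already act as a new-or-worsened table.** Treatment-emergent events are tabulated by system organ class and preferred term, with eye disorders separate, and worsening of a pre-existing condition counts. This stands, and it confines the gap to findings below the threshold in protocol 8.3.1. A reader might infer from SAP 10.6 that new eye findings on treatment would go unseen. The adverse-event tables and the listings contradict that. The listings do not give a between-arm count without hand assembly over about 160 subjects and two eyes.
- **The table specification is not visible.** SAP 12.1 lists the main tables, but its contents are not shown. A shift table may exist there. The point is therefore about what Section 10.6 states.
- **Ophthalmoscopy is different.** A reader might extend the dilution argument to the fundus. The documents do not support that: the background is corneal, and protocol 5.2 excludes "History of diabetic retinopathy, diabetic macular edema, or dry or wet macular degeneration" and other clinically significant ocular disease that might interfere. With little background, by-visit counts lose little.
- **The corneal background is expected, not required.** Criterion 2 names likely subjects. It would be wrong to infer that the trial selects for corneal abnormality.
- **By-visit denominators are ordinary reporting, and randomization balances baseline findings in expectation.** Both are true. The Day 1 table by arm would show an imbalance, but neither fact identifies new findings.
- **No commitment is broken.** Protocol 9.3.6 promises no particular summary of these examinations.

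**Conclusion.** The point holds in a limited form. SAP 10.6, the only visible analysis text for these examinations, states by-visit results without change or eye, where Sections 10.3 to 10.5 state change from baseline. For biomicroscopy, with post-LASIK corneas, scars and keratoconus expected, such tables do not determine how many subjects in each arm developed a new or worsened finding. What is lost is an arm-level count of new findings that are asymptomatic, judged not clinically significant and untreated.

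The size cannot be fixed from the documents, because baseline prevalence is not given. It runs from nothing at zero background to a substantial loss of information at 30% to 50%.

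A reader might also build a sharper case from p-values. With 68 per arm, 50% abnormal and persisting, and 6 new findings on active against 0 on placebo, Day 15 shows 40/68 versus 34/68 (Fisher p = 0.39), while new findings are 6/34 versus 0/34 (p = 0.025). That should not be read as evidence that a significant harm would be missed. The prevalence and counts are assumed, 5 versus 0 already gives p = 0.053, and the plan does not test these data.

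This does not touch the primary analysis. It is a cheap improvement to safety reporting.

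**What to change.** Amend SAP 10.6 to add, by treatment group:

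- a Day 1 to Day 15 shift table for each structure, separately for the study eye and the non-study eye, in subjects with both examinations;
- the number and percent of subjects with a new or worsened finding relative to Day 1 in either eye, descriptive only.

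Keep the by-visit counts. Use the same format for ophthalmoscopy for consistency; the main gain is for biomicroscopy. If SAP 12.1 already lists such a table, refer to it in 10.6 so that text and table list agree.

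The cost is a sentence or two in the SAP and one or two extra descriptive tables. Both examinations are already scheduled at Visit 1 and Visit 3, so no procedure, visit or sample-size figure changes.

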10.7. Other Safety Measures

Urine pregnancy tests for females of childbearing potential will be presented in by-subject listings. Dry eye tests (TearLabs osmolarity test, tear break-up time and cornea fluorescein staining), performed only at Day 1, will also be listed.

12. APPENDICES

[figure not shown]
12.1. List of Planned Tables

[figure not shown]
The list of planned tables includes all of the *main* tables to be presented for the study.

[figure not shown]

[figure not shown]

12.2. List of Planned Listings

12.3. Hierarchy of Sequential Testing
